### **5.2.3.2 Prohibited Therapy**

#### **JAK Inhibitor**

Prior exposure to JAK inhibitors (including but not limited to tofacitinib [Xeljanz®], baricitinib, and filgotinib) is not allowed.

### **Corticosteroids**

Oral corticosteroids > 10 mg prednisone/day or equivalent are NOT allowed up to Week 26. Intra-articular, intramuscular, intravenous, trigger point or tender point, intra-bursa, and intra-tendon sheath corticosteroids are NOT allowed up to Week 26.

### **Biologic Therapies**

All biologic therapies are prohibited during the study (i.e., Periods 1 and 2).

Subjects with prior exposure to at most one bDMARD may be enrolled (up to 20% of study population) if they have a) limited exposure (< 3 months), OR b) response to a bDMARD but had to discontinue that bDMARD due to intolerability (regardless of treatment duration). Of note: prior exposure to adalimumab (Humira®) is not permitted.

Subjects must have discontinued the bDMARD prior to the first dose of study drug as specified in the washout procedures (Inclusion Criterion 8, Section 5.2.1). For all other bDMARDs, contact the Therapeutic Area Medical Director for the washout period required prior to the first dose of study drug.

Examples of biologic therapies include but are not limited to the following:

- Enbrel® (etanercept)
- Remicade® (infliximab)
- Orencia® (abatacept)
- Kineret® (anakinra)
- Rituxan® (rituximab)
- Cimzia® (certolizumab pegol)
- Simponi® (golimumab)
- Actemra® (tocilizumab)
- Raptiva® (efalizumab)
- Tysabri® (natalizumab)
- Stelara® (ustekinumab)

- Benlysta® (belimumab)

### **csDMARD Therapies**

Except MTX, subjects must have discontinued all csDMARDs prior to the first dose of study drug as specified in the washout procedures (Inclusion Criterion 9, Section 5.2.1). csDMARD background therapy other than MTX is not allowed during Period 1.

### **Strong CYP3A Inhibitors or Inducers**

Systemic use of known strong CYP3A inhibitors or strong CYP3A inducers is excluded from the Screening Visit through the end of the study (i.e., Periods 1 and 2). The most common strong CYP3A inhibitors and inducers are listed in [Table 1](#).

**Table 1. Examples of Commonly Used Strong CYP3A Inhibitors and Inducers**

Strong CYP3A Inhibitors	Strong CYP3A Inducers
Boceprevir	Carbamazepine
Cobicistat	Phenytoin
Clarithromycin	Rifampin
Conivaptan	Rifapentine
Grapefruit (fruit or juice)	St. John's Wort
Indinavir	
Itraconazole	
Ketoconazole	
Lopinavir/Ritonavir	
Mibefradil	
Nefazodone	
Nelfinavir	
Posaconazole	
Ritonavir	
Saquinavir	
Telaprevir	
Telithromycin	
Troleandomycin	
Voriconazole	

### **Opiates**

High potency opiates are not permitted during the study (i.e., Periods 1 and 2), and subjects must have discontinued high potency opiates at least 1 week prior to the first dose of study drug, including (but not limited to):

- oxycodone
- oxymorphone
- fentanyl
- levorphanol
- buprenorphine
- methadone
- hydromorphone
- morphine
- meperidine

### **Investigational Drugs**

Subjects who have been treated with any investigational drug within 30 days or five half-lives of the drug (whichever is longer) prior to the first dose of study drug are excluded from participation in this study. Investigational drugs are also prohibited during the study.

### **Vaccines**

Vaccines recommended by local guidelines should be considered. If the investigator chooses to administer a vaccine, this should be completed before first dose of study drug with appropriate precautions and time interval. It is recommended that subjects be up to date for recommended inactivated, toxoid or biosynthetic vaccines, such as injectable flu vaccine, pneumococcal, and pertussis (Tdap). It is recommended that the live herpes zoster vaccine should be considered for administration at least 4 weeks before first dose of study drug or administered at least 30 days after last dose of oral study drug, or at least 70 days after the last dose of subcutaneous study drug. If the herpes zoster vaccine is to

be administered, and there is no known history of primary varicella (chicken pox), pre-existing immunity to varicella should be confirmed with antibody testing at or prior to screening and prior to administration of the herpes zoster vaccine. If screening varicella antibody testing is negative the herpes zoster vaccine should not be administered.

If the subject and investigator choose to administer live vaccines, these vaccinations must be completed (per local label) 4 weeks before first dose of study drug with appropriate precautions, or administered at least 30 days after last dose of oral study drug, or at least 70 days after last dose of subcutaneous study drug.

Examples of live vaccines include, but are not limited to, the following:

- Monovalent live influenza A (H1N1) (intranasal);
- Seasonal trivalent live influenza (intranasal);
- Herpes zoster;
- Rotavirus;
- Varicella (chicken pox);
- Measles-mumps-rubella or measles mumps rubella varicella;
- Oral polio vaccine;
- Smallpox;
- Yellow fever;
- Bacille Calmette-Guérin (BCG);
- Typhoid.

Examples of common vaccines that are inactivated, toxoid or biosynthetic, include but are not limited to: injectable influenza vaccine, pneumococcal and pertussis (Tdap) vaccines.

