  - $\geq 1$  year for rituximab OR  $\geq 6$  months if B cells have returned to pre-treatment level or normal reference range (central lab) if pre-treatment levels are not available.
9. Except for MTX, subject must have discontinued all csDMARDs. The washout period for csDMARDs prior to the first dose of study is specified below or should be at least five times the mean terminal elimination half-life of a drug:
  - $\geq 4$  weeks prior to first dose of study drug for minocycline, penicillamine, sulfasalazine, hydroxychloroquine, chloroquine, azathioprine, gold formulations, cyclophosphamide, tacrolimus, cyclosporine, mycophenolate;\*
  - $\geq 8$  weeks prior to first dose of study drug for leflunomide if no elimination procedure was followed, or adhere to an elimination procedure (i.e., 11 days with colestyramine, or 30 days washout with activated charcoal or as per local label).

\* Additional local requirements may apply. Refer to [Appendix C](#) for local requirements (Korea.)
10. Subjects must have discontinued all high-potency opiates at least 1 week and oral traditional Chinese medicine for at least 4 weeks prior to the first dose of study drug (refer to Section 5.2.3.2 for prohibited medications).
11. Women of childbearing potential (refer to Section 5.2.4), must not have a positive serum pregnancy test at the Screening Visit and must have a negative urine pregnancy test at the Baseline Visit prior to study drug dosing. Note: subjects with borderline serum pregnancy test at Screening must have a serum pregnancy test  $\geq 3$  days later to document continued lack of a positive result.

12. If female, subject must be postmenopausal, OR permanently surgically sterile, OR for women of childbearing potential practicing at least one protocol-specified method of birth control (refer to Section 5.2.4), that is effective from Study Day 1 through at least 150 days after the last dose of subcutaneous study drug and 30 days after the last dose of oral study drug.
  - Additional local requirements may apply. Refer to [Appendix C](#) for local requirements (Canada and Korea.)
13. If male, and subject is sexually active with female partner(s) of childbearing potential, he must agree, from Study Day 1 through 30 days after the last dose of oral study drug, to practice the protocol-specified contraception (refer to Section 5.2.4).
  - Additional local requirements may apply. Refer to [Appendix C](#) for local requirements (Canada and Korea.)

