  - HCV: HCV ribonucleic acid (RNA) detectable in any subject with anti-HCV antibody (HCV Ab).
  - HIV: confirmed positive anti-HIV antibody (HIV Ab) test.
9. Subject has active TB or meets TB exclusionary parameters (refer to Section 5.3.1.1 for specific requirements for TB testing).
  10. Systemic use of known strong cytochrome P450 (CYP)3A inhibitors or strong CYP3A inducers from Screening through the end of the study (refer to Table 1 for examples of commonly used strong CYP3A inhibitors and inducers).
  11. Receipt of any live vaccine within 4 weeks prior to the first dose of study drug, or expected need of live vaccination during study participation including at least 4 weeks after the last dose of oral study drug and including at least 70 days after the last dose of subcutaneous study drug.
  12. History of any malignancy except for successfully treated NMSC or localized carcinoma in situ of the cervix.
  13. History of clinically significant (per Investigator's judgment) drug or alcohol abuse within the last 6 months.
  14. History of gastrointestinal perforation (other than appendicitis or penetrating injury), diverticulitis or significantly increased risk for GI perforation per investigator judgment.
  15. Conditions that could interfere with drug absorption including but not limited to short bowel syndrome.
  16. History of demyelinating disease such as Multiple Sclerosis.
  17. Subject has been a previous recipient of an organ transplant.

18. History of clinically significant medical conditions or any other reason that in the opinion of the Investigator would interfere with the subject's participation in this study or would make the subject an unsuitable candidate to receive study drug.
19. Active infection(s) requiring treatment with parenteral anti-infectives within 30 days, or oral anti-infectives within 14 days prior to the first dose of study drug.
20. History of an allergic reaction or significant sensitivity to constituents of the study drug(s) (and their excipients) and/or other products in the same class.
21. Laboratory values meeting the following criteria within the Screening period prior to the first dose of study drug:
  - Serum aspartate transaminase (AST)  $> 2 \times$  ULN;
  - Serum alanine transaminase (ALT)  $> 2 \times$  ULN;
  - Estimated glomerular filtration rate (GFR) by simplified 4-variable Modification of Diet in Renal Disease (MDRD) formula  $< 40$  mL/min/1.73m^2;

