### 6.1.4 Adverse Event Collection Period

All AEs reported from the time of study drug administration until 70 days following discontinuation of subcutaneous study drug administration and until 30 days following the discontinuation of oral study drug administration have elapsed will be collected, whether solicited or spontaneously reported by the subject. Subjects who discontinue study drug treatment but continue to participate in the study will have SAEs and non-serious AEs collected for the remainder of the study participation. In addition, SAEs and protocol-related nonserious AEs will be collected from the time the subject signed the study-specific informed consent.

Adverse event information will be collected as shown in [Figure 5](#).

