10.2 Analysis of Adverse Events

A treatment-emergent Adverse Event (TEAE) is defined as an adverse event with an onset date that is after the first dose of study drug, and no more than 30 days or 5 half-lives of the drug, whichever is larger, after the last dose of study drug. Specifically, 30 days will be used for Upadacitinib and placebo, and 70 days will be used for ADA.

Events where the onset date is the same as the study drug start date are assumed to be treatment-emergent, unless the study drug start time and the adverse event start time are collected and the adverse event start time is prior to the study drug start time. If an incomplete onset date was collected for an adverse event, the event will be assumed to be treatment-emergent unless there is other evidence that confirms that the event was not treatment-emergent (e.g., the event end date was prior to the study drug start date).

Adverse event data will be presented by SOC and PTs using MedDRA version 19.0 or most up to date version. All adverse event tables will be sorted in alphabetical order by SOC and PT and descending percentages for each treatment group.

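### The live-vaccine rule in Protocol 5.2.3.2 joins its oral and subcutaneous waiting times with *or*, so for a blinded subject the literal text is met 30 days after the last tablet, usually before the 70-day injection interval ends

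*Protocol*

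**What the plan says.** Protocol 5.2.3.2, under Vaccines, has two sentences on live vaccines around the treatment period.

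- The general sentence is binding. If a live vaccine is chosen, "these vaccinations must be completed (per local label) 4 weeks before first dose of study drug", or else it is to be "administered at least 30 days after last dose of oral study drug, or at least 70 days after last dose of subcutaneous study drug".
- The herpes zoster sentence just before it is a recommendation, with the same structure: "administered at least 30 days after last dose of oral study drug, or at least 70 days after the last dose of subcutaneous study drug".

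Elsewhere the protocol joins the two products' intervals with *and*:

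- Section 5.2.2, exclusion criterion 11, on expected need for live vaccination: "at least 4 weeks after the last dose of oral study drug and including at least 70 days after the last dose of subcutaneous" treatment.
- Section 5.2.1, inclusion criterion 12, on contraception: "at least 150 days after the last dose of subcutaneous study drug and 30 days after the last dose of oral study drug".
- Section 6.1.4, on adverse event collection: "until 70 days following discontinuation of subcutaneous study drug administration and until 30 days following the discontinuation of oral study drug administration have elapsed".

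Section 5.1 (Overall Study Design and Plan) gives every subject oral drug daily and an injection every other week until unblinding. Section 5.5.4 requires both products to be stopped when study treatment is withdrawn. Section 5.5.5.1 keeps sites and subjects blinded until the last subject completes Week 48.

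**The concern.** In the binding sentence the first *or* separates two true alternatives: vaccinate before the first dose, or after the last. The second *or* follows in the same construction, so the ordinary reading is that any one limb suffices. Nothing in the sentence says that the later date governs, or that each limb applies to its own product.

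In a single-product trial this would do no harm. Here each blinded subject is on both products and normally stops both together, so the 30-day limb is met first. While blinded, the investigator does not ordinarily know whether the injections were adalimumab or placebo. Subjects who stop study drug may remain in the study (Section 5.1), so a site may still be working from this protocol when the vaccine question comes up.

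What is at stake is a safety instruction whose literal wording allows a live vaccine before the protocol's own waiting time after an injection has ended. The efficacy analyses are not involved.

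**Working it through.** The plan states no figure for this overlap, so there is nothing to reproduce first. The check is date arithmetic.

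Inputs:
- oral interval 30 days, subcutaneous interval 70 days (Protocol 5.2.3.2);
- injections every 14 days, both products stopped together (Protocol 5.5.4);
- up to 2 consecutive missed injections tolerated in the first 26 weeks and up to 3 afterwards (Protocol 5.5.4).

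Take the last tablet as day 0, and let L be the number of days by which the last injection precedes it. The oral interval ends on day 30 and the subcutaneous interval on day 70 − L. For L up to 40, the literal *or* is met on day 30. The shortfall against the subcutaneous interval is

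shortfall = max(0, (70 − L) − 30) = max(0, 40 − L).

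| Injections before stopping | L (days) | Subcutaneous interval ends (day) | Shortfall at day 30 (days) |
|---|---|---|---|
| On schedule | 0 to 14 | 70 to 56 | 40 to 26 |
| One missed | 14 to 28 | 56 to 42 | 26 to 12 |
| Two missed | 28 to 42 | 42 to 28 | 12 to 0 |
| Three missed | 42 to 56 | 28 to 14 | 0 |

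A worked case for a subject who ends treatment at Week 48: injections fall on Day 1 + 14k, and the last tablet is on Day 336, the day before the Week 48 visit (Day 337). The last scheduled injection is on Day 1 + 14 × 23 = Day 323. So L = 336 − 323 = 13, and the shortfall is 40 − 13 = 27 days.

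If both intervals must have passed, the earliest vaccination for on-schedule subjects moves from day 30 to between day 56 and day 70.

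**The case against.** The strongest reply is that each limb names its own product, so the sentence already means 30 days for the tablets and 70 days for the injections. On the either-limb reading, the 70-day limb would do nothing for a subject who stops both products together with injections on schedule. Exclusion criterion 11 also shows that the sponsor had both intervals in mind. In addition, Section 5.4.1 leaves care after discontinuation to the investigator's clinical judgment.

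Most of this stands as evidence of intent, and many sites probably read the rule that way. It does not repair the sentence:

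- The Follow-Up Period text in Section 5.1 joins the same two products with *or*, but pairs each interval with its product by an explicit *respectively*. Appendix C (Canada) says outright that the longest applicable interval governs. The vaccine sentence has neither device.
- Criterion 11 screens for expected need at entry. It does not govern a vaccination decided on after treatment stops.
- Clinical judgment does not correct a stated minimum interval.

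Two stronger readings are tempting, and the documents support neither. First, a reader might take 26 to 40 days as the general size of the gap. It holds only with blinded dosing of both products, a joint stop and on-schedule injections. Second, SAP 10.2 states that "30 days will be used for Upadacitinib and placebo, and 70 days will be used for ADA", under a rule of "no more than 30 days or 5 half-lives of the drug, whichever is larger". A reader might derive a half-life from this, estimate the drug remaining at day 30 and infer a vaccine risk. But that rule defines treatment-emergent adverse events. The documents give no elimination model for adalimumab and no residual level at which live vaccination is unsafe.

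**Conclusion.** The point holds as a wording defect in an operative safety rule, and it is worth a low-priority correction. The 26 to 40 days, and the smaller figures after missed injections, rest on two assumptions: the subject is on both products, and both stop together. The first figure also needs injections on schedule.

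The practical reach is narrow. It covers only subjects whose injections were active: the 300 planned for adalimumab at randomization, plus upadacitinib subjects rescued to it. Of these, it matters only for those who want a live vaccine within weeks of stopping. The documents give no count, and the number is probably small. For a subject long on a single open-label product, the *or* can be read as applying to that product and the gap does not arise.

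The text does not show that the sponsor intends vaccination at 30 days after a recent adalimumab injection. The sections that use *and* point the other way.

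**What to change.** In both sentences of the Vaccines text, replace the *or* between the two intervals with *and*, and add that the later date governs. A live vaccine then waits until 30 days have passed since the last tablet and 70 days since the last injection. Apply this to all injections while the assignment is blinded. After unblinding, the 70 days may be limited to subjects who received adalimumab, because a subject known to have had only placebo injections has no documented reason to wait. A clarification letter to sites would serve equally well.

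The cost is a few words. While blinded, subjects on placebo injections wait up to 40 days longer than under the literal *or*. A site that already requires both intervals changes nothing, and no analysis is touched.

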### **Traditional Chinese Medicine**

Traditional oral Chinese medicine is not permitted during the study as these may interfere with upadacitinib metabolism and exposure and may impact efficacy and safety of

upadacitinib treatment. Subjects must have discontinued traditional Chinese medicine at least 4 weeks prior to the first dose of study drug.

### **5.2.3.3 Rescue Therapy**

Rescue therapy will be offered to subjects who meet the following criteria:

#### **Placebo:**

- Subjects who do not achieve a  $\geq 20\%$  improvement in TJC and SJC at Weeks 14, 18, or 22 compared to baseline will be switched to blinded upadacitinib treatment.
- At Week 26, all remaining subjects will be switched to blinded upadacitinib treatment regardless of clinical response.

#### **ADA:**

- Subjects who do not achieve a  $\geq 20\%$  improvement in TJC and SJC at Weeks 14, 18, or 22 compared to baseline will be switched to blinded upadacitinib treatment.
- At Week 26, all remaining subjects who do not achieve LDA according to CDAI (LDA defined as  $CDAI \leq 10$ ) at Week 26 will be switched to blinded upadacitinib treatment.

#### **Upadacitinib:**

- Subjects who do not achieve a  $\geq 20\%$  improvement in TJC and SJC at Weeks 14, 18, or 22 compared to baseline will be switched to blinded ADA treatment.
- At Week 26, all remaining subjects who do not achieve LDA according to CDAI (LDA defined as  $CDAI \leq 10$ ) at Week 26 will be switched to blinded ADA treatment.

## 5.2.4 Contraception Recommendations

### Contraception Recommendation for Females

A woman who is postmenopausal or permanently surgically sterile (bilateral oophorectomy, bilateral salpingectomy or hysterectomy) is not considered to be a woman of childbearing potential and is not required to follow contraception recommendations. Postmenopausal is defined as:

- Age  $\geq$  55 years with no menses for 12 or more months without an alternative medical cause; or
- Age  $<$  55 years with no menses for 12 or more months without an alternative medical cause AND an FSH level  $>$  40 mIU/mL.

If the female subject is  $<$  55 years of age and is not permanently surgically sterile, as defined above, and has had no menses for  $\geq$  12 months FSH should be tested at Screening.

- If FSH is not tested, it is assumed that the subject is of childbearing potential and protocol-specified contraception is required.
- If the FSH is tested and the result is consistent with post-menopausal status, contraception is not required.
- If the FSH is tested and the result is consistent with pre-menopausal status, contraception is required, and a serum pregnancy test must be performed (see Section 5.3.1.1 pregnancy test).

For a female subject at any age:

- Female subjects with menses within the past 12 months are of childbearing potential and FSH is therefore not required but contraception is required.
- Female subjects who are surgically sterile (defined above) are not of childbearing potential and therefore no FSH testing or contraception is required.

A woman who does not meet the definition of postmenopausal or permanently surgically sterile is considered of childbearing potential and is required to practice at least one of the following highly effective methods of birth control that is effective from Study Day 1 (or earlier) through at least 150 days after the last dose of subcutaneous study drug and at least 30 days after the last dose of oral study drug.

- Combined (estrogen and progestogen containing) hormonal contraception (oral, intravaginal, transdermal) associated with the inhibition of ovulation, initiated at least 30 days prior to Study Day 1.
- Progestogen-only hormonal contraception (oral, injectable, implantable) associated with inhibition of ovulation, initiated at least 30 days prior to Study Day 1.
- Bilateral tubal occlusion/ligation.
- Vasectomized partner(s), provided the vasectomized partner has received medical confirmation of the surgical success and is the sole sexual partner of the women of childbearing potential trial participant.
- Intrauterine device (IUD).
- Intrauterine hormone-releasing system (IUS).
- True abstinence: Refraining from heterosexual intercourse when this is in line with the preferred and usual lifestyle of the subject (periodic abstinence [e.g., calendar, ovulation, symptothermal, post-ovulation methods] and withdrawal are not acceptable).

If required per local practices, male or female condom with or without spermicide OR cap, diaphragm or sponge with spermicide should be used in addition to one of the highly effective birth control methods listed above (excluding true abstinence).

It is important to note that contraception recommendations described above are specifically intended to prevent pregnancy during exposure to the investigational therapies. Duration of contraception after discontinuation of csDMARDs should be based on the local label.

If during the course of the study a woman becomes surgically sterile or post-menopausal and complete documentation is available, contraception measures as defined above are no longer required.

Additional local requirements may apply. Refer to Appendix C for local requirements (Canada and Korea).

